9.7.1 Sample Size**Table 6: Power (%) to Detect Safety Events**

| Event Frequency | N=30 | N=180 |
|------------------------|-------------|--------------|
| ≥10% Very Common | 95 | >99 |
| ≥1% Common | 26 | 83 |
| ≥0.1% Uncommon | 2 | 16 |
| ≥0.01% Rare | <1 | 1 |

Table 7: Precisions of Binomial Confidence Intervals

| N | 95% CI |
|----------|---------------|
| 30 | 31-69 |
| 180 | 42-58 |

Table 8: Minimum Detectable Difference in Proportion Responders

| N per Group | Proportion Responders in Comparator Group A | 80% Power | |
|-------------|---|-------------------------------|---|
| | | Minimal Detectable Difference | Proportion Responders in Comparator Group B |
| N=27 | 0.10 | 0.32 | 0.42 |
| | 0.20 | 0.35 | 0.55 |
| | 0.30 | 0.38 | 0.68 |
| | 0.40 | 0.37 | 0.77 |
| | 0.50 | 0.34 | 0.84 |

10.2 Protocol Deviations

Table 9: Distribution of Protocol Deviations by Category, Type, and Study Group

| Category | Deviation Type | Group 1 2013 3.75+AS03/ 2017 3.75+AS03 (D1-D22) (N=X) | | Group 2 2013 3.75+AS03/ 2017 3.75+AS03 (D1-D121) (N=X) | | Group 3 2013 3.75+AS03/ 2017 15 (D1-D121) (N=X) | | Group 4 2017 3.75+AS03/ 2017 3.75+AS03 (D1-D22) (N=X) | | Group 5 2017 3.75+AS03/ 2017 3.75+AS03 (D1-D121) (N=X) | | Group 6 2017 3.75+AS03/ 2017 15 (D1-D121) (N=X) | | All Subjects (N=X) | |
|---|---|---|--------------|--|--------------|--|--------------|---|--------------|--|--------------|--|--------------|-----------------------|--------------|
| | | # of Subj. | # of Dev. | # of Subj. | # of Dev. | # of Subj. | # of Dev. | # of Subj. | # of Dev. | # of Subj. | # of Dev. | # of Subj. | # of Dev. | # of Subj. | # of Dev. |
| Eligibility/ enrollment | Any type | | | | | | | | | | | | | | |
| | Did not meet inclusion criterion | x | x | x | x | x | x | x | x | x | x | x | x | x | x |
| | Met exclusion criterion | | | | | | | | | | | | | | |
| | ICF not signed prior to study procedures | | | | | | | | | | | | | | |
| | Other | | | | | | | | | | | | | | |
| Treatment administration schedule | Any type | | | | | | | | | | | | | | |
| | Out of window visit | | | | | | | | | | | | | | |
| | Missed visit/visit not conducted | | | | | | | | | | | | | | |
| | Missed treatment administration | | | | | | | | | | | | | | |
| | Delayed treatment administration | | | | | | | | | | | | | | |
| | Other | | | | | | | | | | | | | | |

| Category | Deviation Type | Group 1 2013 3.75+AS03/ 2017 3.75+AS03 (D1-D22) (N=X) | | Group 2 2013 3.75+AS03/ 2017 3.75+AS03 (D1-D121) (N=X) | | Group 3 2013 3.75+AS03/ 2017 15 (D1-D121) (N=X) | | Group 4 2017 3.75+AS03/ 2017 3.75+AS03 (D1-D22) (N=X) | | Group 5 2017 3.75+AS03/ 2017 3.75+AS03 (D1-D121) (N=X) | | Group 6 2017 3.75+AS03/ 2017 15 (D1-D121) (N=X) | | All Subjects (N=X) | |
|--------------------------------------|--|---|--------------|--|--------------|--|--------------|---|--------------|--|--------------|--|--------------|-----------------------|--------------|
| | | # of Subj. | # of Dev. | # of Subj. | # of Dev. | # of Subj. | # of Dev. | # of Subj. | # of Dev. | # of Subj. | # of Dev. | # of Subj. | # of Dev. | # of Subj. | # of Dev. |
| Follow-up visit schedule | Any type | | | | | | | | | | | | | | |
| | Out of window visit | | | | | | | | | | | | | | |
| | Missed visit/visit not conducted | | | | | | | | | | | | | | |
| | Other | | | | | | | | | | | | | | |
| Protocol procedure/ assessment | Any type | | | | | | | | | | | | | | |
| | Incorrect version of ICF signed | | | | | | | | | | | | | | |
| | Blood not collected | | | | | | | | | | | | | | |
| | Urine not collected | | | | | | | | | | | | | | |
| | Other specimen not collected | | | | | | | | | | | | | | |
| | Too few aliquots obtained | | | | | | | | | | | | | | |
| | Specimen result not obtained | | | | | | | | | | | | | | |
| | Required procedure not conducted | | | | | | | | | | | | | | |
| | Required procedure done incorrectly | | | | | | | | | | | | | | |

| Category | Deviation Type | Group 1 2013 3.75+AS03/ 2017 3.75+AS03 (D1-D22) (N=X) | | Group 2 2013 3.75+AS03/ 2017 3.75+AS03 (D1-D121) (N=X) | | Group 3 2013 3.75+AS03/ 2017 15 (D1-D121) (N=X) | | Group 4 2017 3.75+AS03/ 2017 3.75+AS03 (D1-D22) (N=X) | | Group 5 2017 3.75+AS03/ 2017 3.75+AS03 (D1-D121) (N=X) | | Group 6 2017 3.75+AS03/ 2017 15 (D1-D121) (N=X) | | All Subjects (N=X) | |
|-------------------------------|-------------------------------------|---|--------------|--|--------------|--|--------------|---|--------------|--|--------------|--|--------------|-----------------------|--------------|
| | | # of Subj. | # of Dev. | # of Subj. | # of Dev. | # of Subj. | # of Dev. | # of Subj. | # of Dev. | # of Subj. | # of Dev. | # of Subj. | # of Dev. | # of Subj. | # of Dev. |
| | Study product temperature excursion | | | | | | | | | | | | | | |
| | Specimen temperature excursion | | | | | | | | | | | | | | |
| | Other | | | | | | | | | | | | | | |
| Treatment administration | Any type | | | | | | | | | | | | | | |
| | Required procedure done incorrectly | | | | | | | | | | | | | | |
| | Study product temperature excursion | | | | | | | | | | | | | | |
| | Other | | | | | | | | | | | | | | |
| Blinding policy/ procedure | Any type | | | | | | | | | | | | | | |
| | Treatment unblinded | | | | | | | | | | | | | | |
| | Other | | | | | | | | | | | | | | |

N = Number of subjects enrolled.

Implementation Note: Shell has placeholders for all types of deviations possible. The final table will be limited to deviations actually reported in the study.

12.2.2 Displays of Adverse Events

Table 10: Solicited Adverse Event Grading Scale – Local

| Local (Injection Site) Reactogenicity Grading | | | |
|---|---|---|--|
| Local (Injection Site) Reaction | Mild (Grade 1) | Moderate (Grade 2) | Severe (Grade 3) |
| Pain – experienced without touching the injection site (spontaneous discomfort) | Subject is aware of pain, but it does not interfere with daily activity, and no pain medication is taken | Subject is aware of pain; there is interference with daily activity, or it requires repeated use of a non-narcotic pain reliever for >24 hours | Subject is aware of pain, and it prevents daily activity or requires any use of a narcotic pain reliever |
| Tenderness – hurts only when injection site is touched, or the arm is moved | The area immediately surrounding the injection site hurts only when touched or with arm motion, and it does not interfere with daily activity | The area immediately surrounding the injection site hurts when touched or with arm motion, and it interferes with daily activity | The area immediately surrounding the injection site hurts when touched or with arm motion, and it prevents daily activity |
| Pruritus (Itching) | Does not interfere with daily activity | Interferes with daily activity | Prevents daily activity |
| Ecchymosis (Bruising)* | Does not interfere with daily activity | Interferes with daily activity | Prevents daily activity |
| Erythema (Redness)* | Does not interfere with daily activity | Interferes with daily activity | Prevents daily activity |
| Induration (Hardness)/Swelling* | Does not interfere with daily activity | Interferes with daily activity | Prevents daily activity |
| Local (Injection Site) Reactogenicity Measurements | | | |
| Local (Injection Site) Reaction | Small (Grade 1) | Medium (Grade 2) | Large (Grade 3) |
| Ecchymosis (Bruising)* | <20 mm | 20 mm – 50 mm | >50 mm |
| Erythema (Redness)* | <20 mm | 20 mm – 50 mm | >50 mm |
| Induration (Hardness)/Swelling* | <20 mm | 20 mm – 50 mm | >50 mm |

Table 11: Solicited Adverse Event Grading Scale - Systemic

| Subjective Systemic Reactogenicity Grading | | | |
|--|--------------------------------------|---------------------------------------|---|
| Systemic (Subjective) | Mild (Grade 1) | Moderate (Grade 2) | Severe (Grade 3) |
| Feverishness (Chills/Shivering/Sweating) | No interference with daily activity | Some interference with daily activity | Significant interference, prevents daily activity |
| Fatigue (Tiredness) | No interference with daily activity | Some interference with daily activity | Significant interference, prevents daily activity |
| Malaise (General Unwell Feeling) | No interference with daily activity | Some interference with daily activity | Significant interference, prevents daily activity |
| Myalgia (Body Aches/Muscular Pain)* | No interference with daily activity | Some interference with daily activity | Significant interference, prevents daily activity |
| Arthralgia (Joint Pain)* | No interference with daily activity | Some interference with daily activity | Significant interference, prevents daily activity |
| Headache | No interference with daily activity | Some interference with daily activity | Significant interference, prevents daily activity |
| Nausea | No interference with daily activity | Some interference with daily activity | Significant interference, prevents daily activity |
| Quantitative Systemic Reactogenicity Grading | | | |
| Systemic (Quantitative) | Mild (Grade 1) | Moderate (Grade 2) | Severe (Grade 3) |
| Fever [#] - oral [†] | 38.0°C – 38.4°C 100.4°F – 101.1°F | 38.5°C – 38.9°C 101.2°F – 102.0°F | >38.9°C >102.0°F |
| 
* Not at injection site.
 
[#] Oral temperature assessed on Day 1 prior to the first study vaccination will be considered as baseline. A fever can be considered not related to the study product if an alternative etiology can be documented.
 | | | |

Table 12: Vital Signs Adverse Event Grading Scale

| Physiologic Parameter | Mild (Grade 1) | Moderate (Grade 2) | Severe (Grade 3) |
|---|-----------------------|---------------------------|-------------------------|
| Bradycardia - beats per minute | 45 – 46 | 40 – 44 | <40 |
| Tachycardia - beats per minute | 101 – 130 | 131 – 155 | >155 |
| Hypotension (systolic) mmHg | 80 – 84 | 75 – 79 | <75 |
| Hypotension (diastolic) mmHg | 50 – 54 | 45 – 49 | <45 |
| Hypertension (systolic) mmHg | 151 – 155 | 156 – 160 | >160 |
| Hypertension (diastolic) mmHg | 96 – 100 | 101 – 105 | >105 |
| # Pulse and blood pressure assessed on Day 1 prior to the first study vaccination will be considered as baseline. | | | |

12.4.1 Individual Laboratory Measurements and Abnormal Laboratory Values**Table 13: Laboratory Adverse Event Grading Scale**

| Hematology | Mild (Grade 1) | Moderate (Grade 2) | Severe (Grade 3) |
|--|---------------------------|-------------------------------|-----------------------------|
| WBC 10 ³ /μL (Decrease) | 2.5 – 3.9 | 1.5 – 2.4 | <1.5 |
| WBC 10 ³ /μL (Increase) | 10.6 – 15.0 | 15.1 – 20.0 | >20.0 |
| Hgb g/dL (Decrease) (Female) | 10.1 – 11.4 | 8.5 – 10 | <8.5 |
| Hgb g/dL (Decrease) (Male) | 11.0 – 12.4 | 9.5 – 10.9 | <9.5 |
| Platelets 10 ³ /μL (Decrease) | 125 – 139 | 100 – 124 | <100 |
| Platelets 10 ³ /μL (Increase) | 416 – 550 | 551– 750 | >750 |
| Chemistry | Mild (Grade 1) | Moderate (Grade 2) | Severe (Grade 3) |
| ALT IU/L (Increase) (Female) | 44 – 100 | 101 – 200 | >200 |
| ALT IU/L (Increase) (Male) | 61 – 138 | 139 – 275 | >275 |
| Total Bilirubin mg/dL (Increase) – when accompanied by any increase in ALT | 1.30 – 1.59 | 1.60 – 1.80 | >1.80 |
| Total Bilirubin mg/dL (Increase) – when ALT is normal | 1.30 – 1.89 | 1.90 – 2.40 | >2.40 |
| Creatinine mg/dL (Increase) (Female) | 1.1 – 1.7 | 1.8 – 2.0 | >2.0 |
| Creatinine mg/dL (Increase) (Male) | 1.4 – 1.7 | 1.8 – 2.0 | >2.0 |

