9.2.2 Reactogenicity

Reactogenicity events are AEs that are common and known to occur following administration of this type of study vaccine. The following Toxicity Grading Scales will be used to grade solicited injection site and systemic (subjective and quantitative) reactions:

Table 6: Injection Site Reactogenicity Grading

Injection Site Reaction	Mild (Grade 1)	Moderate (Grade 2)	Severe (Grade 3)
Pain – experienced without touching the injection site (spontaneous discomfort)	Subject is aware of pain, but it does not interfere with daily activity, and if pain medication is used, it is Over the Counter (OTC) and used for less than 24 hours	Subject is aware of pain; there is interference with daily activity or OTC pain medication is used for more than 24 hours	Subject is aware of pain, and it prevents daily activity or pain requires prescription medication
Tenderness – hurts only when injection site is touched or the arm is moved	The area immediately surrounding the injection site hurts only when touched or with arm motion, and it does not interfere with daily activity	The area immediately surrounding the injection site hurts when touched or with arm motion, and it interferes with daily activity	The area immediately surrounding the injection site hurts when touched or with arm motion, and it prevents daily activity
Pruritus (Itching)	Does not interfere with daily activity	Interferes with daily activity	Prevents daily activity
Ecchymosis (Bruising)*	Does not interfere with daily activity	Interferes with daily activity	Prevents daily activity
Erythema (Redness)*	Does not interfere with daily activity	Interferes with daily activity	Prevents daily activity
Induration (Hardness)/Edema (Swelling)*	Does not interfere with daily activity	Interferes with daily activity	Prevents daily activity

* Will also be measured in mm but size will not be used as halting criteria.

Ecchymosis, erythema and induration (hardness)/edema (swelling) as analyzed by measurement will be graded as follows:

Table 7: Injection Site Reactogenicity Measurements

Injection Site Reaction	Small	Medium	Large
Ecchymosis (Bruising)*	<20 mm	20 mm – 50 mm	>50 mm
Erythema (Redness)*	<20 mm	20 mm – 50 mm	>50 mm
Induration (Hardness)/Edema (Swelling)*	<20 mm	20 mm – 50 mm	>50 mm

* Will not be used as halting criteria.

Table 8: Subjective Systemic Reactogenicity Grading

Systemic (Subjective)	Mild (Grade 1)	Moderate (Grade 2)	Severe (Grade 3)

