| | Moderate | x | xx (xx-xx) | x | xx (xx-xx) | x | xx (xx-xx) | x | xx (xx-xx) | x | xx (xx-xx) | x | xx (xx-xx) | x | xx (xx-xx) |
| | Severe | x | xx (xx-xx) | x | xx (xx-xx) | x | xx (xx-xx) | x | xx (xx-xx) | x | xx (xx-xx) | x | xx (xx-xx) | x | xx (xx-xx) |

N = Number of subjects in the Safety Population who received any study vaccination; n = Number of subjects reporting event.

95% CI estimated using Clopper-Pearson exact method.

Severity is the maximum severity reported over all solicited symptoms post dosing for each subject.

Tables with similar format:

Table 90: Number and Percentage of Subjects Experiencing Solicited Events by Symptom, Maximum Severity and Study Group (Safety Population) – Post Study Vaccination 1

[Footnote Update] N = Number of subjects in the Safety Population who received the first study vaccination = Number of subjects reporting event.

Table 91: Number and Percentage of Subjects Experiencing Solicited Events by Symptom, Maximum Severity and Study Group (Safety Population) – Post Study Vaccination 2

[Footnote Update] N = Number of subjects in the Safety Population who received the second study vaccination; n = Number of subjects reporting event.

Table 92: Number and Percentage of Subjects Experiencing Solicited Events by Symptom, Severity, Day Post Study Vaccination, and Study Group (Safety Population) – Post Any Study Vaccination

| Symptom | Severity | Pre-Vac | | Post-Vac | | Day 1 | | Day 2 | | Day 3 | | Day 4 | | Day 5 | | Day 6 | | Day 7 | | Day 8+ | |
|---|----------|---------|----|----------|----|-------|----|-------|----|-------|----|-------|----|-------|----|-------|----|-------|----|--------|----|
| | | n | % | n | % | n | % | n | % | n | % | n | % | n | % | n | % | n | % | n | % |
| Group 1: 2013 3.75+AS03/ 2017 3.75+AS03 (D1-D22) (N=X) | | | | | | | | | | | | | | | | | | | | | |
| Any Symptom | None | x | xx | x | xx | x | xx | x | xx | x | xx | x | xx | x | xx | x | xx | x | xx | x | xx |
| | Mild | x | xx | x | xx | x | xx | x | xx | x | xx | x | xx | x | xx | x | xx | x | xx | x | xx |
| | Moderate | x | xx | x | xx | x | xx | x | xx | x | xx | x | xx | x | xx | x | xx | x | xx | x | xx |
| | Severe | x | xx | x | xx | x | xx | x | xx | x | xx | x | xx | x | xx | x | xx | x | xx | x | xx |
| Any Systemic Symptom | None | x | xx | x | xx | x | xx | x | xx | x | xx | x | xx | x | xx | x | xx | x | xx | x | xx |

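### SAP Table 10 grades injection-site pain by a different medication rule from the protocol and relabels reaction size as Grade 1 to 3, which affects the solicited local severity tables

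*SAP*

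**What the plan says.** **Pain.** In Protocol 9.2.2, Table 6, pain without interference is Grade 1, and "if pain medication is used, it is Over the Counter (OTC) and used for less than 24 hours". Grade 2 is interference, or that "OTC pain medication is used for more than 24 hours". Grade 3 is that "it prevents daily activity or pain requires prescription medication". In SAP Table 10, Grade 1 means that "it does not interfere with daily activity, and no pain medication is taken". Grade 2 is interference, or that "it requires repeated use of a non-narcotic pain reliever for >24 hours". Grade 3 is that "it prevents daily activity or requires any use of a narcotic pain reliever".

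**Size.** Protocol Table 7 classes ecchymosis, erythema and induration/swelling as Small (<20 mm), Medium (20 to 50 mm) or Large (>50 mm), with no grade numbers. The same reactions have a functional Grade 1 to 3 in Table 6, and Protocol 9.5 keeps size out of the halting rules. SAP Table 10 keeps the cut-offs but labels them Grade 1, 2 and 3. The SAP Table 89 shell has separate '(measurement)' rows with the categories None, Mild, Moderate and Severe, and its footnote reads: "Severity is the maximum severity reported over all solicited symptoms post dosing for each subject". Tables 90 and 91 share that format.

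**Status.** SAP 4.5.1 and 9.3.1 point to Table 10 as the local grading scale. Protocol 9.2.1 has a study physician assess severity on the protocol's own grading system. SAP section 12 states that nothing departs from the protocol's analyses.

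**The concern.** Solicited reactogenicity is a primary safety outcome, and Protocol 11.6.2 asks for it by severity, by day and as a maximum. Those tables can be read only if the printed scale is the one under which the grades were assigned. If sites graded pain by the protocol, the report will print definitions that do not describe its own counts. If Table 10 was used, the counts depart from the protocol without a declared change. For size, the shell leaves open whether a large reaction with no effect on activity is counted as severe in the two summary rows that readers look at first.

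**Working it through.** The plan states no figure on this point, so the check sets the two scales side by side.

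**Pain.** Take 3 levels of interference (none, some, prevents activity) and 7 medication patterns (none; then OTC, non-narcotic prescription or narcotic, each for under or over 24 h). That gives 3 × 7 = 21 patterns. Each receives the highest grade whose definition it meets. Assumptions: OTC products are non-narcotic, narcotics are prescription drugs, use over 24 h counts as repeated, and taking a drug counts as requiring it.

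| Interference | Medication | Protocol Table 6 | SAP Table 10 |
|---|---|---|---|
| None | OTC, under 24 h | Grade 1 | no grade fits |
| None | Non-narcotic prescription, under 24 h | Grade 3 | no grade fits |
| None | Non-narcotic prescription, over 24 h | Grade 3 | Grade 2 |
| Some | Non-narcotic prescription, under 24 h | Grade 3 | Grade 2 |
| Some | Non-narcotic prescription, over 24 h | Grade 3 | Grade 2 |

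The other 21 − 5 = 16 patterns agree. The first row fails the SAP's Grade 1 because a drug was taken, and fails its Grade 2 because there is neither interference nor use beyond 24 h.

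**Other rows.** Tenderness, pruritus, ecchymosis, erythema and induration/swelling have the same functional grades in both documents. The 20 mm and 50 mm cut-offs also match.

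**Size.** Take redness over 50 mm that does not interfere with activity.

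- Protocol: functional Grade 1 (Table 6), size Large (Table 7).
- SAP: functional row Mild, measurement row Severe.
- 'Any Local Symptom' if measurement rows enter the maximum: max(1, 3) = 3, Severe.
- 'Any Local Symptom' if they do not: max(1) = 1, Mild.

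The SAP does not say which applies. The footnote's wording covers every solicited symptom, and the measurement rows stand in the symptom column. In both cases the maximum is at least 1, so the subject counts as having an event.

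**Size of effect.** One subject moved into or out of Severe changes an arm's rate by 1/30 = 3.3 percentage points (30 subjects per arm, all with data).

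**The case against.** Most of the local scale is unaffected: one of six functional rows differs, and the size cut-offs are identical. The primary outcome is worded as occurrence. The protocol's binary analysis is none versus any grade, and the SAP's logistic models count any event of Grade 1 or higher. These are largely untouched. This stands, and it confines the point to severity.

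It can also be said that Table 10 is only a reference display. No SAP rule re-derives a pain grade from medication use, and SAP Listing 12 takes severity from the staff-reviewed Memory Aid or the clinic assessment. If sites followed the protocol, the counts keep their protocol meaning and only the printed definitions are wrong. That is fair, and the documents do not include the forms that would settle it. It does not remove the contradiction, because SAP 4.5.1 and 9.3.1 name Table 10 as the scale.

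On size, the protocol itself speaks of grading by measurement, excludes size only from halting, and the SAP already gives size its own rows. A reader might infer that large redness without functional effect will certainly be counted as severe. The documents do not support that: the SAP is silent on whether measurement rows feed the summary rows, and only a literal reading of the footnote leads there.

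A reader might also infer that halting or second-dose decisions are affected. They are not. Those rules sit in Protocol 9.5 and 5.2.3, and SAP 6.6.1 refers back to Protocol 9.5.

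Finally, 5 of 21 is a count of logical patterns, not of subjects. Four of the five need a non-narcotic prescription for pain that does not prevent activity.

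**Conclusion.** The point holds within these limits. The pain row of SAP Table 10 contradicts Protocol Table 6 at Grades 1 and 3, and section 12 does not declare it. Separately, the SAP turns size categories into severity labels and leaves open whether they enter the maximum for 'Any Local Symptom' and 'Any Symptom'; read literally, they do. Both affect the severity tables for solicited local events. The any-versus-none results and the halting and second-dose rules are not shown to change.

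The number of subjects affected cannot be known from the documents; each would be 3.3 percentage points in an arm of 30. The count of differing patterns rests on the drug-class assumptions stated above. The documents do not show which pain scale the data collection forms carried, and nothing here says which is clinically preferable.

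**What to change.** 1. Reconcile the two pain rows. SAP Table 10 should reproduce the scale under which the sites assigned grades, confirmed from the Memory Aid and data collection forms. If that is not the Protocol Table 6 scale, record the difference in SAP section 12.
2. Keep the existing measurement rows, but label their categories Small, Medium and Large as in Protocol Table 7, in SAP Table 10 and in every solicited-event shell that shows severity.
3. Add to SAP 9.3.1 and the Table 89 footnote that maximum severity for 'Any Local Symptom' and 'Any Symptom' is taken over the functional grades only.

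The cost is table text and one derivation rule. No new data or extra analysis is needed.

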14.1 Description of Study Subjects

14.1.1 Disposition of Subjects

Table 14: Ineligibility Summary of Screen Failures

| Category | Criterion | n^a | %^b |
|----------------------------------|--|----------------------|----------------------|
| Inclusion and Exclusion | Number of subjects failing any eligibility criterion | x | x |
| Inclusion | Any inclusion criterion | x | x |
| | [inclusion criterion 1] | x | x |
| | [inclusion criterion 2] | x | x |
| | [inclusion criterion 3] | x | x |
| Exclusion | Any exclusion criterion | x | x |
| | [exclusion criterion 1] | x | x |
| | [exclusion criterion 2] | x | x |
| | [exclusion criterion 3] | x | x |
| Eligible but Not Enrolled | Any reason | x | x |
| | [reason 1] | x | x |

^a More than one criterion may be marked per subject.
^b Denominator for percentages is the total number of screen failures.

Table 15: Analysis Populations by Study Group – All Enrolled Subjects

[Implementation Note: Only include reasons actually reported, omit lines for any reasons that were not observed in the trial.]

| Analysis Populations | Reason Subjects Excluded | Group 1 2013 3.75+AS03/ 20173.75+AS03 (D1-D22) (N=X) | | Group 2 2013 3.75+AS03/ 2017 3.75+AS03 (D1-D121) (N=X) | | Group 3 2013 3.75+AS03/ 2017 15 (D1-D121) (N=X) | | Group 4 2017 3.75+AS03/ 2017 3.75+AS03 (D1-D22) (N=X) | | Group 5 2017 3.75+AS03/ 2017 3.75+AS03 (D1-D121) (N=X) | | Group 6 2017 3.75+AS03/ 2017 15 (D1-D121) (N=X) | | All Subjects (N=X) | |
|---------------------------------|---|---|----|--|----|--|----|---|----|--|----|--|----|--------------------------|----|
| | | n | % | n | % | n | % | n | % | n | % | n | % | n | % |
| Safety Population | Any Reason | x | xx | x | xx | x | xx | x | xx | x | xx | x | xx | x | xx |
| | Study Vaccination 1 Not Received | x | xx | x | xx | x | xx | x | xx | x | xx | x | xx | x | xx |
| Modified Intent-to-Treat | Any Reason | x | xx | x | xx | x | xx | x | xx | x | xx | x | xx | x | xx |
| | Study Vaccination 1 Not Received | x | xx | x | xx | x | xx | x | xx | x | xx | x | xx | x | xx |
| | No Baseline Results Available | x | xx | x | xx | x | xx | x | xx | x | xx | x | xx | x | xx |
| | No Post-Vaccination Results Available | x | xx | x | xx | x | xx | x | xx | x | xx | x | xx | x | xx |
| Per Protocol, Day 22 post Vac 1 | Any Reason | x | xx | x | xx | x | xx | x | xx | x | xx | x | xx | x | xx |
| | Study Vaccination 1 Not Received | x | xx | x | xx | x | xx | x | xx | x | xx | x | xx | x | xx |
| | No Baseline Results Available | x | xx | x | xx | x | xx | x | xx | x | xx | x | xx | x | xx |
| | No Day 22 post Vac 1 Result Reported by Lab | x | xx | x | xx | x | xx | x | xx | x | xx | x | xx | x | xx |
| | Lost to Follow-up Before Day 22 post Vac 1 | x | xx | x | xx | x | xx | x | xx | x | xx | x | xx | x | xx |
| | Receipt of Non-Study Vaccination | x | xx | x | xx | x | xx | x | xx | x | xx | x | xx | x | xx |
| | Receipt of Immunosuppressive medication | x | xx | x | xx | x | xx | x | xx | x | xx | x | xx | x | xx |

| Analysis Populations | Reason Subjects Excluded | Group 1 2013 3.75+AS03/ 20173.75+AS03 (D1-D22) (N=X) | | Group 2 2013 3.75+AS03/ 2017 3.75+AS03 (D1-D121) (N=X) | | Group 3 2013 3.75+AS03/ 2017 15 (D1-D121) (N=X) | | Group 4 2017 3.75+AS03/ 2017 3.75+AS03 (D1-D22) (N=X) | | Group 5 2017 3.75+AS03/ 2017 3.75+AS03 (D1-D121) (N=X) | | Group 6 2017 3.75+AS03/ 2017 15 (D1-D121) (N=X) | | All Subjects (N=X) | |
|----------------------------------|--|---|----|--|----|--|----|---|----|--|----|--|----|--------------------------|----|
| | | n | % | n | % | n | % | n | % | n | % | n | % | n | % |
| | Day 22 post Vac 1 Visit Out of Window | x | xx | x | xx | x | xx | x | xx | x | xx | x | xx | x | xx |
| Per Protocol, Day 121 post Vac 1 | Any Reason | NA | NA | x | xx | x | xx | NA | NA | x | xx | x | xx | x | xx |
| | Study Vaccination 1 Not Received | NA | NA | x | xx | x | xx | NA | NA | x | xx | x | xx | x | xx |
| | Study Vaccination 2 Not Received | NA | NA | x | xx | x | xx | NA | NA | x | xx | x | xx | x | xx |
| | Study Vaccination 2 Out of Window | NA | NA | x | xx | x | xx | NA | NA | x | xx | x | xx | x | xx |
| | No Baseline Results Available | NA | NA | x | xx | x | xx | NA | NA | x | xx | x | xx | x | xx |
| | No Day 121 post Vac 1 Result Reported by Lab | NA | NA | x | xx | x | xx | NA | NA | x | xx | x | xx | x | xx |
| | Lost to Follow-up Before Day 121 post Vac 1 | NA | NA | x | xx | x | xx | NA | NA | x | xx | x | xx | x | xx |
| | Receipt of Non-Study Vaccination | NA | NA | x | xx | x | xx | NA | NA | x | xx | x | xx | x | xx |
| | Receipt of Immunosuppressive medication | NA | NA | x | xx | x | xx | NA | NA | x | xx | x | xx | x | xx |
| | Day 121 post Vac 1 Visit Out of Window | NA | NA | x | xx | x | xx | NA | NA | x | xx | x | xx | x | xx |
| Per Protocol, Day 22 post Vac 2 | Any Reason | x | xx | x | xx | x | xx | x | xx | x | xx | x | xx | x | xx |
| | Study Vaccination 1 Not Received | x | xx | x | xx | x | xx | x | xx | x | xx | x | xx | x | xx |
| | Study Vaccination 2 Not Received | x | xx | x | xx | x | xx | x | xx | x | xx | x | xx | x | xx |

| Analysis Populations | Reason Subjects Excluded | Group 1 2013 3.75+AS03/ 20173.75+AS03 (D1-D22) (N=X) | | Group 2 2013 3.75+AS03/ 2017 3.75+AS03 (D1-D121) (N=X) | | Group 3 2013 3.75+AS03/ 2017 15 (D1-D121) (N=X) | | Group 4 2017 3.75+AS03/ 2017 3.75+AS03 (D1-D22) (N=X) | | Group 5 2017 3.75+AS03/ 2017 3.75+AS03 (D1-D121) (N=X) | | Group 6 2017 3.75+AS03/ 2017 15 (D1-D121) (N=X) | | All Subjects (N=X) | |
|----------------------------------|--|---|----|--|----|--|----|---|----|--|----|--|----|--------------------------|----|
| | | n | % | n | % | n | % | n | % | n | % | n | % | n | % |
| | Study Vaccination 2 Out of Window | x | xx | x | xx | x | xx | x | xx | x | xx | x | xx | x | xx |
| | No Baseline Results Available | x | xx | x | xx | x | xx | x | xx | x | xx | x | xx | x | xx |
| | No Day 22 post Vac 2 Result Reported by Lab | x | xx | x | xx | x | xx | x | xx | x | xx | x | xx | x | xx |
| | Lost to Follow-up Before Day 22 post Vac 2 | x | xx | x | xx | x | xx | x | xx | x | xx | x | xx | x | xx |
| | Receipt of Non-Study Vaccination | x | xx | x | xx | x | xx | x | xx | x | xx | x | xx | x | xx |
| | Receipt of Immunosuppressive medication | x | xx | x | xx | x | xx | x | xx | x | xx | x | xx | x | xx |
| | Day 22 post Vac 2 Visit Out of Window | x | xx | x | xx | x | xx | x | xx | x | xx | x | xx | x | xx |
| Per Protocol, Day 181 post Vac 2 | Any Reason | x | xx | x | xx | x | xx | x | xx | x | xx | x | xx | x | xx |
| | Study Vaccination 1 Not Received | x | xx | x | xx | x | xx | x | xx | x | xx | x | xx | x | xx |
| | Study Vaccination 2 Not Received | x | xx | x | xx | x | xx | x | xx | x | xx | x | xx | x | xx |
| | Study Vaccination 2 Out of Window | x | xx | x | xx | x | xx | x | xx | x | xx | x | xx | x | xx |
| | No Baseline Results Available | x | xx | x | xx | x | xx | x | xx | x | xx | x | xx | x | xx |
| | No Day 181 post Vac 2 Result Reported by Lab | x | xx | x | xx | x | xx | x | xx | x | xx | x | xx | x | xx |

| Analysis Populations | Reason Subjects Excluded | Group 1 2013 3.75+AS03/ 20173.75+AS03 (D1-D22) (N=X) | | Group 2 2013 3.75+AS03/ 2017 3.75+AS03 (D1-D121) (N=X) | | Group 3 2013 3.75+AS03/ 2017 15 (D1-D121) (N=X) | | Group 4 2017 3.75+AS03/ 2017 3.75+AS03 (D1-D22) (N=X) | | Group 5 2017 3.75+AS03/ 2017 3.75+AS03 (D1-D121) (N=X) | | Group 6 2017 3.75+AS03/ 2017 15 (D1-D121) (N=X) | | All Subjects (N=X) | |
|----------------------|---|---|----|--|----|--|----|---|----|--|----|--|----|--------------------------|----|
| | | n | % | n | % | n | % | n | % | n | % | n | % | n | % |
| | Lost to Follow-up Before Day 181 post Vac 2 | x | xx | x | xx | x | xx | x | xx | x | xx | x | xx | x | xx |
| | Receipt of Non-Study Vaccination | x | xx | x | xx | x | xx | x | xx | x | xx | x | xx | x | xx |
| | Receipt of Immunosuppressive medication | x | xx | x | xx | x | xx | x | xx | x | xx | x | xx | x | xx |
| | Day 181 post Vac 2 Visit Out of Window | x | xx | x | xx | x | xx | x | xx | x | xx | x | xx | x | xx |

Table 16: Subject Disposition by Study Group, All Enrolled Subjects

| Subject Disposition | Group 1 2013 3.75+AS03/ 2017 3.75+AS03 (D1-D22) (N=X) | | Group 2 2013 3.75+AS03/ 2017 3.75+AS03 (D1-D121) (N=X) | | Group 3 2013 3.75+AS03/ 2017 15 (D1-D121) (N=X) | | Group 4 2017 3.75+AS03/ 2017 3.75+AS03 (D1-D22) (N=X) | | Group 5 2017 3.75+AS03/ 2017 3.75+AS03 (D1-D121) (N=X) | | Group 6 2017 3.75+AS03/ 2017 15 (D1-D121) (N=X) | | All Subjects (N=X) | |
|--|---|-----|--|-----|---|-----|---|-----|--|-----|---|-----|-----------------------|-----|
| | n | % | n | % | n | % | n | % | n | % | n | % | n | % |
| Screened | x | -- | x | -- | x | -- | x | -- | x | -- | x | -- | x | -- |
| Enrolled/Randomized | x | 100 | x | 100 | x | 100 | x | 100 | x | 100 | x | 100 | x | 100 |
| Received Vaccination 1 | x | xx | x | xx | x | xx | x | xx | x | xx | x | xx | x | xx |
| Received Vaccination 2 | x | xx | x | xx | x | xx | x | xx | x | xx | x | xx | x | xx |
| Received All Scheduled Vaccinations ^a | x | xx | x | xx | x | xx | x | xx | x | xx | x | xx | x | xx |
| Completed Blood Draw for Primary Immunogenicity Analysis ^b | x | xx | x | xx | x | xx | x | xx | x | xx | x | xx | x | xx |
| Included in Per Protocol Immunogenicity Analysis of Primary Immunogenicity Outcomes ^{b c} | x | xx | x | xx | x | xx | x | xx | x | xx | x | xx | x | xx |
| Completed Primary Follow-up ^{a b c} | x | xx | x | xx | x | xx | x | xx | x | xx | x | xx | x | xx |
| Completed Final Study Visit ^b | x | xx | x | xx | x | xx | x | xx | x | xx | x | xx | x | xx |

N=Number of subjects enrolled.

^a Refer to Listing 2 for reasons subjects discontinued from study vaccinations or terminated early.

^b The final blood draw for Primary Immunogenicity Analysis occurs at 21 days post final vaccination (Day 43 for Groups 1 and 4; Day 142 for Groups 2, 3, 5 and 6).

^c Refer to Listing 5 for reasons subjects are excluded from the Per Protocol Population.

Table 17: Dates of First Study Vaccination by Site and Study Group

| Dates of Dosing | Group 1 2013 3.75+AS03/ 2017 3.75+AS03 (D1-D22) (N=X) | Group 2 2013 3.75+AS03/ 2017 3.75+AS03 (D1-D121) (N=X) | Group 3 2013 3.75+AS03/ 2017 15 (D1-D121) (N=X) | Group 4 2017 3.75+AS03/ 2017 3.75+AS03 (D1-D22) (N=X) | Group 5 2017 3.75+AS03/ 2017 3.75+AS03 (D1-D121) (N=X) | Group 6 2017 3.75+AS03/ 2017 15 (D1-D121) (N=X) | All Subjects (N=X) |
|---|--|---|--|--|---|--|-------------------------------|
| [Site 1] | | | | | | | |
| Total (Entire period of enrollment) | x | x | x | x | x | x | x |
| DDMMYYYYY-DDMMYYYYY | x | x | x | x | x | x | x |
| | | | | | | | |
| [Site 2] | | | | | | | |
| Total (Entire period of enrollment) | x | x | x | x | x | x | x |
| DDMMYYYYY-DDMMYYYYY | x | x | x | x | x | x | x |
| | | | | | | | |
| [Repeat for all sites] | | | | | | | |
| N= Number of subjects in the Safety Population. | | | | | | | |

Table with similar format:

Table 18: Dates of Second Study Vaccination by Site and Study Group

